## **6. Outcome Measures**

➤ **Primary Outcome Measures:**

(1) Treatment success at one year

Treatment success at 12 months after antiarrhythmic drug (AAD) initiation or ablation utilizing cryoballoon catheter measured by freedom from AF recurrence following a 3-month period after the index ablation or AAD initiation.

The primary outcome was time to first documented recurrence of symptomatic or asymptomatic atrial tachyarrhythmia (AF, atrial flutter, or atrial tachycardia)

(2) Rate of serious adverse events

Rate of complications and adverse events occurred during cryoballoon ablation and postoperative follow-up, including procedure-related complications such as bleeding, phrenic nerve palsy (PNP), cerebral embolism, pericardial effusion/tamponade, atriopharyngeal fistula, and all-cause mortality, re-hospitalization for HF, and the composite event of all-cause mortality or HF hospitalization.

➤ **Secondary Outcome Measures**

(1) Quality of life changes at 12 months measured by AF Quality of Life Survey (AFEQT)

The improvement in quality of life between baseline and 12 months after the index ablation procedure or AAD measured by AFEQT is evaluated.

(2) Quality of life changes at 12 months measured by 12-Item Short Form Survey (SF-12)

The improvement in quality of life between baseline and 12 months after the index ablation procedure or AAD measured by SF-12 is evaluated.

(3) Arrhythmia recurrence during blanking period (Time Frame: 3 months)

Atrial tachycardia recurrence rate during the blanking period is evaluated.

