### 2. Study Design

Study Type	Interventional (Clinical Trial)
Estimated Enrollment:	200 participants
Allocation:	No-Randomized
Intervention Model:	Parallel Assignment
Primary Purpose:	Treatment
Estimated Study Start Date:	May 1,2022
Estimated Primary Completion Date:	December 31, 2023
Estimated Study Completion Date:	June 1, 2024

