Post-ablation, all patients had in-office Follow-up visit at discharge. A subset of patients reconsented for 1, 3, 6, and 12-month follow-up visits. On follow-up visits physical examination was performed, a 12-lead electrocardio gram (ECG) and 24-h Holter monitor were recorded, and medication changes were documented. In addition, regular telephone interviews were performed. Additional outpatient clinic visits were immediately initiated in cases of symptoms suggestive of recurrent arrhythmia. Repeat ablation was offered to the patient in cases of symptomatic AF/AT recurrence after the blanking period or symptomatic drug-refractory recurrent AF/AT within the blanking period that could not be managed without intervention. Furthermore, LVEF and the NYHA score were systematically evaluated at follow-up on TTE.

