## **7. Statistical analysis**

(1) All statistical analyses were performed using SPSS version 22.0 software (SPSS, Chicago, IL, USA).

(2) All continuous variables were recorded as mean  $\pm$  standard deviation (SD). Categorical variables were presented as numbers or percentages. Between-group comparisons were performed using t-test, Mann–Whitney test, or Chi-square test. Fisher’s exact test was used when the observed value in any of the 2 $\times$ 2 contingency table cells was  $<5$ . Continuous variables were compared among groups using one-way analysis of variance or Kruskal–Wallis test.

(3) The effect of variables on the EF value was analyzed by univariate and multivariate logistic regression analyses. Baseline clinical features, medical history, and clinical and

laboratory parameters on admission were considered as candidate variables in the multivariate analysis.

(4) The association between the EF group and the outcomes was assessed using univariable and multivariable Cox analyses. Variables of relevant clinical interest considered as covariates were included in the multivariable model to identify the predictors for adverse outcomes according to EF category.

(5) A 2-sided p value less than 0.05 was considered as statistically significant.

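### Primary outcome (1) is given two conflicting event sets: AF alone, then AF, atrial flutter or atrial tachycardia

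*Combined protocol and SAP*

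**What the plan says.** Section 6, primary outcome (1), has two consecutive sentences.

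- The first describes treatment success at 12 months, "measured by freedom from AF recurrence following a 3-month period after the index ablation or AAD initiation". The event is AF, counted after a 3-month blank, with a 12-month horizon.
- The second reads "The primary outcome was time to first documented recurrence of symptomatic or asymptomatic atrial tachyarrhythmia (AF, atrial flutter, or atrial tachycardia". It names three arrhythmias and repeats neither the blank nor the horizon.

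Two other places bear on the event set. Secondary outcome (3) in section 6 is titled as arrhythmia recurrence, but its text says "Atrial tachycardia recurrence rate during the blanking period is evaluated". Section 5.2 (Post-procedure) says "Repeat ablation was offered to the patient in cases of symptomatic AF/AT recurrence after the blanking period".

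Section 7 assigns no method to primary outcome (1). Item (2) is generic: "Between-group comparisons were performed using t-test", followed by Mann–Whitney and chi-square. Item (4) says "The association between the EF group and the outcomes was assessed using univariable and multivariable Cox analyses".

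**The concern.** The second sentence lists AF as one of three separate arrhythmias, so the two sentences do not describe the same event on their face. A patient with only atrial flutter or atrial tachycardia after month 3 is classified in opposite ways.

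This is the primary effectiveness outcome. With both wordings in place, either event set could be reported as primary once the data are known, and a reader could not tell whether that choice was made in advance. The comparison of ablation with drug treatment would also change if isolated flutter or tachycardia is not equally common in the two groups.

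**Working it through.** **Step 1: the two sentences side by side.**

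| | First sentence | Second sentence |
|---|---|---|
| Event | AF | AF, atrial flutter or atrial tachycardia |
| Form | Status at 12 months | Time to first event |
| 3-month blank | Stated | Not repeated |
| 12-month horizon | Stated | Not repeated |
| Only AF after month 3 | Failure | Event |
| Only flutter or tachycardia after month 3 | Success | Event |

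The last row is the contradiction.

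**Step 2: does anything else settle it?** Section 5.2 refers to AF/AT, but only as a trigger for offering repeat ablation. Secondary (3) names atrial tachycardia alone, which is a third term. Section 7 ties no test to this outcome, and its Cox model is for EF group. No text says which event set governs.

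**Step 3: size.** The document has no figure to reproduce: it gives 200 participants but no recurrence rates, power or allocation ratio. All rates below are assumptions.

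- Share with arrhythmia in months 0–3: e = 0.20–0.40, of whom half recur later.
- Share of the remaining patients who recur later: l0 = 0.20–0.30.
- Late recurrence = 0.5e + (1 − e) × l0. Low: 0.10 + 0.80 × 0.20 = 0.26. High: 0.20 + 0.60 × 0.30 = 0.38.
- Share of late recurrences that are flutter or tachycardia only: f = 0.10–0.20.

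Twelve-month success:

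- All three arrhythmias: 1 − late = 0.62 to 0.74.
- AF only: 1 − late × (1 − f). Low: 1 − 0.38 × 0.90 = 0.658. High: 1 − 0.26 × 0.80 = 0.792.
- Gap in the same patients = late × f. Low: 0.26 × 0.10 = 0.026. High: 0.38 × 0.20 = 0.076. Times 200, this is 5.2 to 15.2 patients.

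Shift in the between-group difference = (late × f) in one group minus (late × f) in the other:

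- Equal in both groups: 0.
- Equal late recurrence, f = 0.20 versus 0.10: 0.026 (late 0.26) to 0.038 (late 0.38). With an assumed 100 per group the standard errors are 0.062 and 0.069, so the ratios are 0.42 and 0.55.
- Opposite extremes: 0.38 × 0.20 − 0.26 × 0.10 = 0.050. The group difference is 0.38 − 0.26 = 12.0 points on the broad set, and 0.304 − 0.234 = 7.0 points on AF only.
- Standard error at the extremes, 100 per group: √(0.26 × 0.74/100 + 0.38 × 0.62/100) = 0.0654. Ratio: 0.050/0.0654 = 0.76. With an assumed 50/150 split, in either direction, the standard error is 0.0736 or 0.0774 and the ratio 0.68 or 0.65.

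**Step 4: what this could do to power.** Assume 100 per group, two-sided 0.05, and AF-only recurrence of 50% on drug and 30% on ablation. Power for the 12-month proportion is 83%. If flutter and tachycardia add 3 points to both groups (53% versus 33%), it is 82%. If they add 3 points on drug and 8 on ablation (53% versus 38%), it is 57%. An equal addition barely matters; an unequal one can. The unequal case puts isolated flutter or tachycardia at 3/53 = 6% and 8/38 = 21% of recurrences, slightly outside the range for f in step 3.

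**The case against.** The best defence is that the intent can be read from the text. The second sentence opens by declaring itself the primary outcome, section 5.2 also goes beyond AF, and terminology is loose enough for AF in the first sentence to be shorthand. The broader set is indeed the likelier intent. But likely intent is not a stated definition, and the second sentence treats AF as one item of three. This part of the conflict stands.

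It is also fair to say that the numbers do not prove harm. Every rate is assumed, and the effect on the treatment comparison may be zero. The case rests on the text and not on the size.

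Four stronger readings are tempting, and the document does not support them.

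- *Status and time to event are incompatible.* They are not: freedom from an event at 12 months can be estimated from time-to-event data by Kaplan–Meier. What is missing is a statement that this is the estimator.
- *The second sentence counts events from day 0.* It is silent on the blank, but secondary (3) handles the blanking period separately and section 5.2 refers to it as well. The blank and the horizon are evidently meant to carry over and need only be restated.
- *Many patients will have no 12-month status, because* "A subset of patients reconsented for 1, 3, 6, and 12-month follow-up visits". That sentence concerns scheduled visits after ablation. The same paragraph provides telephone interviews and extra visits for suggestive symptoms, so it shows reduced monitoring and not early exit.
- *Secondary (3) confirms the broader set.* Literally it names atrial tachycardia and leaves AF out. It shows inconsistent terminology only.

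**Conclusion.** The point holds for the event set. Primary outcome (1) has two definitions that classify the same patient in opposite ways, and no text says which applies. This is a contradiction in a primary outcome and should be resolved before analysis.

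On the assumed rates, reported 12-month success depends on the definition by 2.6–7.6 points. The treatment difference moves by 0 to 5.0 points, at most 0.76 standard errors with 100 per group, so a change in statistical significance is plausible only for a result that close to the threshold. The direction is unknown, because the document does not say how often isolated flutter or tachycardia is expected in either group.

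The missing estimator, the unrepeated blank and horizon, and the wording of secondary (3) are gaps to close in the same edit, not further contradictions in the primary outcome.

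**What to change.** **Section 6.**

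- Give one definition for both groups: time from the index procedure or the start of the antiarrhythmic drug to the first documented episode of AF, atrial flutter or atrial tachycardia later than month 3, followed to month 12.
- Report 12-month success as the Kaplan–Meier estimate of freedom from that same event.
- Keep AF-only recurrence as a sensitivity analysis.
- Use the same arrhythmia set in secondary (3).
- State how the analysis treats deaths before month 12 and repeat ablation within the blanking period. Section 5.2 allows the latter, and section 7 addresses neither.

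**Section 7.** Name the time-to-event comparison of ablation with drug treatment for this outcome, since item (4) covers EF group only. Allocation is "No-Randomized", so baseline adjustment is a related question, but a separate one from this definition.

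**Cost.** The change is rewording in section 6 and a short addition to section 7; the definition itself needs no new data. Reported success will be lower than with AF-only counting, by 2.6–7.6 points under the assumptions above. Rewording does not cure unequal rhythm monitoring: section 5.2 describes scheduled ECG and Holter visits after ablation for a reconsented subset, and section 5.1 gives no schedule for the medical group. That should be stated as a separate limitation.

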### 3. Study subjects

Subjects with atrial fibrillation and heart failure with different ejection fraction categories are divided to either an anti-arrhythmic drug or cryoballoon catheter pulmonary vein isolation.

(1) Medical treatment group: receive class I or class III AAD to restore or maintain sinus rhythm; Antiarrhythmic drug including Propafenone, Sotalol, Dronedaron and

Amiodarone;

(2) Experimental: cryoballoon ablation group receive cryoballoon ablation to restore sinus rhythm; Pulmonary vein isolation by cryoballoon ablation using Medtronic Arctic Front Advance™ Cardiac CryoAblation Catheters (23mm and 28mm);

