##### **➤ Exclusion Criteria:**

- (1) History of AF treatment with class I or III AAD, including sotalol, with the intention to prevent an AF recurrence. However, patients pretreated with above AAD for less than 7 days with the intention to convert an AF episode are allowed;
- (2) Previous left atrial ablation;
- (3) Previous cardiac surgery including prosthetic valves;
- (4) Permanent pacemaker or defibrillator implant;
- (5) Second degree type II or third-degree AV-block or a pattern of left/right bundle branch block;
- (6) History of previous myocardial infarction or percutaneous intervention during the last 3 months;
- (7) Any history of previous transient ischemic attack, prolonged reversible ischemic neurological deficit, and/or stroke;
- (8) Known intracardiac thrombus formation;
- (9) Pulmonary vein stent;
- (10) Known cryoglobulinaemia;
- (11) Active systemic infection;
- (12) Hypertrophic cardiomyopathy;
- (13) Life expectancy is  $\leq 1$  year;
- (14) Reversible cause of atrial fibrillation (eg, hyperthyroidism or alcoholism);
- (15) Abnormal long or short QT intervals, signs of Brugada syndrome, known family history of inherited ion channel disease, and/or arrhythmogenic right ventricular dysplasia;

- 
- (16) Chronic obstructive pulmonary disease with detected pulmonary hypertension and/or any other evidence of significant lung disease;
  - (17) Contraindication for oral anticoagulation;
  - (18) Pregnant women or woman of childbearing potential with inadequate birth control;
  - (19) Women who are breastfeeding;
  - (20) Any significant congenital heart defect corrected or not corrected; however, patent foramen ovale is allowed;
  - (21) Thrombocytosis (platelet count > 600,000 / $\mu$ L) or thrombocytopenia (platelet count < 100,000 / $\mu$ L);
  - (22) Untreated or uncontrolled hyperthyroidism or hypothyroidism;
  - (23) Renal dysfunction with glomerular filtration rate < 60 mL/min;
  - (24) Unstable angina pectoris;
  - (25) Symptomatic carotid stenosis;
  - (26) Myxoma based on laboratory abnormalities;
  - (27) Sarcoidosis;
  - (28) Unwilling to unable to comply with the study procedure and follow-up schedule due to any disease condition;
  - (29) Legal incapacity or evidence that the patient cannot understand the purpose and risks of the study, including inability to comply fully with study procedures and follow-up;
  - (30) Employed by Medtronic, or the department of an investigator, or close-familial relative of an investigator;

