## **5. Study Process**

### **5.1 Medical treatment group**

Patients admitted to the medical treatment group after screening could receive electrocardiography and receive class I or class III AAD to restore or maintain sinus rhythm. The survey included variables that concern the baseline characteristics of patients, including risk factors, clinical history, cardiac diagnosis, electrocardiogram, echocardiography, laboratory blood tests, and treatments. All patients were symptomatic (functional NYHA class II–IV) and were treated according to contemporary clinical guidelines.

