## 5.2 Cryoballoon ablation group

### ➤ Pre-procedure

In addition to survey contents for medical treatment group, the Transesophageal echocardiography (TEE) was performed in all patients prior to the procedure. The echocardiographic parameters include left ventricular ejection fraction (LVEF), peak early trans-mitral inflow velocity/peak late mitral inflow velocity ratio (E/A), left atrial diameter (LAD), LV end-diastolic diameter (LVEDD), and LV mass. All recordings were performed and analyzed by the same investigator. In patients on vitamin K antagonists, anticoagulation was continued throughout the procedure, aiming at an international normalized ratio (INR) of 2-3. In patients treated with novel oral anticoagulants (NOACs), the drug was discontinued 12-24 hour prior to the procedure and re-initiated 6-hour post-ablation at half the regular dose, and then at full dose on the following day.

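### Death and HF hospitalisation are counted only from the ablation procedure onward, and no analysis set covers patients assigned to ablation but not ablated, so selective loss from the ablation group cannot be excluded

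*Combined protocol and SAP*

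**What the plan says.** - **Allocation.** Section 2 gives it as "No-Randomized", with "200 participants" and no split by group. Section 3 says that subjects "are divided to either an anti-arrhythmic drug or cryoballoon catheter pulmonary vein isolation", without a rule for who goes where. It describes the ablation arm by its procedure: "cryoballoon ablation group receive cryoballoon ablation to restore sinus rhythm".
- **Entry to the drug group.** Section 5.1: "Patients admitted to the medical treatment group after screening could receive electrocardiography and receive class I or class III AAD". Its baseline survey includes echocardiography but does not mention a TEE.
- **Entry to the ablation group.** Section 5.2, Pre-procedure, adds to that survey: "the Transesophageal echocardiography (TEE) was performed in all patients prior to the procedure". It does not say what follows if the TEE shows thrombus.
- **Thrombus exclusion.** Exclusion (8) in Section 4 applies to both groups and reads "Known intracardiac thrombus formation".
- **Primary (1).** Section 6 measures "freedom from AF recurrence following a 3-month period after the index ablation or AAD initiation". The event is a documented atrial tachyarrhythmia; death is not an event.
- **Primary (2).** Section 6 covers events during the ablation and the postoperative follow-up. The list includes all-cause mortality, re-hospitalisation for HF and their composite. No period is given for the drug group.
- **Analysis.** Section 7 states no analysis set, no time origin for the Cox models, and no rule for patients who do not receive the treatment they were assigned.

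**The concern.** In a non-randomised comparison, the groups should at least be fixed and followed from comparable moments. Here the ablation clock cannot start until a patient has had a TEE and reached the procedure. A patient assigned to ablation who has thrombus on the TEE, is admitted for HF or dies beforehand has no index ablation, no described follow-up visits and no window in which primary (2) events count. The plan has no place for that patient.

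If such patients are at higher risk than the rest and have no counterpart removed from the drug group, the ablation group looks healthier with no treatment effect at all. Death and HF hospitalisation would be affected most. The loss depends on what happens between assignment and treatment, so adjustment for baseline covariates can remove only the part that measured baseline factors explain.

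**Working it through.** **Step 1. Trace a patient through the text.**

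| Situation | Assigned to ablation | Assigned to drug |
|---|---|---|
| Thrombus unknown at screening | Looked for by TEE before the clock starts; consequence not stated | No TEE listed; patient stays in |
| Death or HF admission before treatment starts | Outside the primary (2) window | Before the primary (1) clock; no primary (2) window stated |
| Never receives the assigned treatment | No index date, no rule | No index date, no rule |

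The first row differs between groups on the face of the text. The second and third rows show loss in both groups. They become unequal only if one group waits longer or more often goes untreated, and the plan gives no waiting time.

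**Step 2. Size if unablated patients are lost.** The plan gives no event rates. Its only planning figure, 200, has no derivation and cannot be reproduced. Assumptions: 100 patients assigned per group; no treatment effect; k of 100 ablation patients not ablated; 12-month risk of death or HF hospitalisation 40% in patients of that kind and 20% in the rest.

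- True rate in both groups = ((100 − k) × 0.20 + k × 0.40) / 100
- Ablation rate after removal = 20%
- Drug rate if the k patients are moved there = (100 × true rate + 0.40 × k) / (100 + k)

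| k | True rate (drug rate if dropped) | False benefit, dropped | Drug rate if moved | False benefit, moved |
|---|---|---|---|---|
| 5 | (19 + 2)/100 = 21% | 1.0 points | 23/105 = 21.9% | 1.9 points |
| 10 | (18 + 4)/100 = 22% | 2.0 points | 26/110 = 23.6% | 3.6 points |
| 15 | (17 + 6)/100 = 23% | 3.0 points | 29/115 = 25.2% | 5.2 points |

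If the k patients carry the same risk as the rest, every false benefit is zero.

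**Step 3. Compare with sampling error.** Near a 22% rate with 100 per group, the standard error of the difference is √(2 × 0.22 × 0.78 / 100) = 0.059, or 5.9 points. The bias is therefore 0.2 to 0.5 standard errors if patients are dropped (1.0/5.9 to 3.0/5.9), and up to 0.9 if all are moved (5.2/5.9).

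**Step 4. Effect on the test.** Now hold the overall risk at 20% in each assigned group, with no true effect and a two-sided 5% two-proportion test.

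| Lost from ablation group | Their risk | Dropped: rates, rejection rate | Moved: rates, rejection rate |
|---|---|---|---|
| 5% | 40% | 18.9% vs 20.0%, 5.4% | 18.9% vs 21.0%, 6.4% |
| 10% | 40% | 17.8% vs 20.0%, 6.7% | 17.8% vs 21.8%, 10.7% |
| 10% | 80% | 13.3% vs 20.0%, 23% | 13.3% vs 25.5%, 57% |

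**Step 5. Events during a wait.** With a constant hazard and an assumed annual risk of death or HF hospitalisation of 10-30%, the share with an event before the ablation clock starts is 1 − (1 − annual risk)^(w/12) for a wait of w months. This gives 0.9-2.9% for one month and 2.6-8.5% for three months.

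**The case against.** The strongest reply is that the plan leaves a rule undefined and does not document a filter. Much of this stands.

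- **Group membership by treatment received.** A reader might infer this from Section 3. Section 5.1, however, speaks of admission to a group after screening, which puts membership before treatment. As-treated grouping is not stated, and neither is removal or transfer of a patient with a positive TEE.
- **Loss from the ablation group alone.** A reader might infer this for deaths and deterioration too. The documents support it only for thrombus found on TEE. A drug patient who dies before the first dose is also lost from primary (1).
- **Transfer to the drug group.** Once a TEE shows thrombus, it is known, and exclusion (8) could be read as barring the patient from the study altogether. A patient who has died cannot be transferred. Moving all 5-15% is thus an upper bound.
- **Timing of the TEE.** It could be part of the work-up before membership is fixed. The loss would then not follow assignment, but an eligibility check would still be applied to one group only.
- **Other outcomes.** A reader might extend the point to quality of life or claim a false benefit on cerebral embolism. Quality of life is measured from baseline, and only its end point is tied to the index. Embolism is listed as a procedure-related complication with no stated drug-group count. Neither extension is supported.

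The reply does not remove the stated window for primary (2). Followed literally, it omits every event before the procedure, and no other section says where an unablated patient is counted.

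**Conclusion.** The point holds as a should-fix. The documents establish a treatment-start clock for primary (1), a primary (2) window that opens at the procedure with no drug-group equivalent, a TEE required in one group only, and no analysis set. Selective removal from the ablation group therefore cannot be excluded. For deaths and HF admissions, an imbalance in favour of ablation further requires a longer wait for ablation than for drug, which is plausible but not stated.

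The size rests wholly on assumed inputs: 1-3 points if 5-15% are dropped at twice the risk of the rest, about 5 points at most if all are moved, and zero at average risk. All of these lie below one standard error. The large distortions in Step 4 need 10% lost at 80% risk. The bias on recurrence has not been quantified. A claim that the comparison is certainly or heavily biased would go beyond the text.

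**What to change.** - Record one assignment date per patient, after consent and baseline and before the TEE. Apply exclusion (8) in both groups according to what is known on that date.
- In the primary analysis, keep every patient in the assigned group, including those whose TEE shows thrombus and those never ablated. This concerns the analysis set only, not clinical care, and needs no TEE in the drug group.
- Restate primary (2) so that death, HF hospitalisation and serious adverse events are counted from assignment over the same period in both groups.
- For recurrence, keep the 3-month blanking period from treatment start, state how never-treated patients and deaths before treatment are handled, and add a sensitivity analysis with time zero at assignment in both groups.
- Report the assignment-to-treatment interval and the number not treated, with reasons, by group. Give a treated-patients analysis as supportive.

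The cost is revised wording in Sections 4, 6 and 7, one extra date field, and an ablation estimate that is likely to be slightly less favourable because unablated patients are kept. The change does not address confounding from non-randomised allocation, which needs its own treatment.

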## Study Protocol and Statistical Analysis Plan

# Cryoballoon Ablation Versus Medical Therapy in Patients with Atrial Fibrillation and Heart Failure with Different Ejection Fraction Categories

### 1. Study objective

This study is to assess the effectiveness and safety of cryoballoon ablation comparing with medical therapy in patients with atrial fibrillation and heart failure with different ejection fraction categories

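### The primary safety outcome is defined only over ablation and its postoperative follow-up, so drug-arm events, including deaths and heart-failure admissions, fall outside it as written

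*Combined protocol and SAP*

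**What the plan says.** Section 1 sets a comparative aim: to "assess the effectiveness and safety of cryoballoon ablation comparing with medical therapy". Section 6 names two primary outcomes. The second is headed "Rate of serious adverse events" and defined as "Rate of complications and adverse events occurred during cryoballoon ablation and postoperative follow-up". The list of included events starts with procedural complications and ends with "all-cause mortality, re-hospitalization for HF, and the composite event of all-cause mortality or HF hospitalization".

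Other outcomes in section 6 are given a start in both arms. Primary outcome (1) counts recurrence "following a 3-month period after the index ablation or AAD initiation". The quality-of-life outcomes do likewise; the first is measured at "12 months after the index ablation procedure or AAD measured by AFEQT".

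On data collection, section 5.1 (medical group) describes baseline assessment and treatment: "The survey included variables that concern the baseline characteristics of patients". Follow-up appears only in the post-procedure part of section 5.2 (ablation group): "Post-ablation, all patients had in-office Follow-up visit at discharge". There, the visits at 1, 3, 6 and 12 months apply to a subset who reconsented. Telephone interviews are also mentioned, again only under the ablation group.

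**The concern.** A comparative safety objective needs events and time at risk in both arms. The window in primary outcome (2) opens with a procedure that drug-arm patients do not undergo. The event list is not what excludes them: death, HF admission, bleeding and cerebral embolism can all occur on drugs. The window excludes them. No harm specific to AAD treatment is named either.

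Two things are at stake. Followed literally, one of the two primary outcomes has no comparator, and the safety half of the objective cannot be met. If the arms were compared anyway, deaths and HF admissions counted after ablation would be set against drug-arm events that were not counted, or only partly counted, which biases the comparison against ablation.

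There is also a mismatch over what is counted. The heading refers to serious events, while the definition covers complications and adverse events in general, and no criterion for seriousness is given.

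**Working it through.** **Reading the text.** The plan states no safety rate, power or arm split, so there is no figure of its own to reproduce. The finding rests on setting the sections side by side.

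| Item | Time origin, ablation arm | Time origin, drug arm |
|---|---|---|
| Primary (1), recurrence | index ablation | AAD initiation |
| Secondary (1) and (2), quality of life | index ablation | AAD |
| Primary (2), safety | ablation and postoperative follow-up | none stated |

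I then looked for text that could fill the empty cell.

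- Section 5.1 gives the drug arm a baseline survey and treatment, with no follow-up and no adverse-event collection.
- Section 5.2 covers procedural complications and post-ablation contacts only.
- Section 7 (2) lists generic between-group tests. Section 7 (4) plans Cox models for outcomes by ejection-fraction group. Neither defines a safety window for the drug arm.

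The cell stays empty. A patient treated only with drugs adds nothing to the numerator or the time at risk.

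**Illustration of size.** Inputs from the document: 200 patients in total (section 2), two-sided 0.05 (section 7 (5)), and Fisher's exact test when any cell of a 2×2 table is below 5 (section 7 (2)). Assumptions of mine: the arm split, the event rates, and zero counted drug-arm events over the full drug-arm denominator.

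Step 1. Find the smallest number of ablation-arm events, k, for which k/n1 against 0/n2 gives two-sided Fisher p < 0.05. For equal arms, p = 2 × C(100,k)/C(200,k). For unequal arms, p sums the probabilities of all tables no more likely than the one observed.

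Step 2. With the same true rate r in both arms, the chance of a false signal against ablation is P(Binomial(n1, r) ≥ k).

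| Ablation/drug | Smallest k (p) | One fewer event (p) | r = 2% | r = 5% | r = 10% |
|---|---|---|---|---|---|
| 100/100 | 6 (0.0289) | 5 (0.0594) | 1.5% | 38% | 94% |
| 120/80 | 7 (0.0432) | 6 (0.0830) | 1.1% | 39% | 96% |
| 80/120 | 4 (0.0245) | 3 (0.0626) | 7.7% | 57% | 96% |

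Step 3. As a benchmark, count events in both arms and take the probability that Fisher p < 0.05 with the higher rate under ablation. Over the three splits this is 0.2% to 1.2% at r = 2%, and 1.0% to 2.0% at r = 5% and 10%. Using uncorrected chi-square when no cell is below 5, as section 7 (2) allows, moves the 100/100, 10% value from 1.4% to 2.3%. The other values change little.

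**The case against.** The best counter-argument is that this is loose drafting. The heading names no arm. Death and HF admission are not procedural events. The objective is comparative, section 7 (2) plans between-group tests, and primary outcome (1) and the quality-of-life outcomes already presuppose 12 months of drug-arm follow-up. The authors may well have meant procedural complications in the ablation arm plus death and HF events in everyone. The event list is also open-ended, so failing to name drug harms does not exclude them.

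That is a fair account of probable intent, but the definition does not say it: death and HF events are listed inside the ablation-anchored sentence. Even on the generous reading, the drug arm has no stated start, end, schedule or method for collecting safety events.

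A second objection is that the illustration describes an error nobody has planned. If the drug-arm rate is undefined, no 2×2 test can be run, and an analyst would have to ignore known drug-arm deaths while keeping those patients in the denominator. Section 7 also specifies no between-arm test for this outcome by name. This stands as a limit on the numbers: zero is the extreme case, partial capture would bias the comparison less, and at a 2% rate the effect is small. The finding does not depend on them.

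Third, the text is mostly in the past tense and section 2 estimates completion on June 1, 2024, so extra prospective contacts may no longer be possible. That bears on the cost of the remedy and leaves the defect in place.

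**Conclusion.** The concern holds and should be fixed before any safety comparison is made. As written, primary outcome (2) has no drug-arm count or time at risk, in direct conflict with the comparative objective in section 1 and out of line with primary outcome (1) and the quality-of-life outcomes. One minor qualification: a drug-arm patient who later had an ablation would enter the window at that point, but the plan gives no rule for such crossover.

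The size cannot be derived from the documents. Under the extreme assumption that no drug-arm events are counted, with equal true rates, a false signal against ablation has a chance of 1.1% to 7.7% at a 2% rate, 38% to 57% at 5% and 94% to 96% at 10%, over splits from 80/120 to 120/80. Symmetric counting gives at most about 2.3%. The direction of bias is clear; its true amount depends on how many drug-arm events are missed.

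**What to change.** - **Window.** Define primary outcome (2) in both arms from index ablation or AAD initiation to 12 months, the clock that primary outcome (1) already uses. Apply the 3-month blanking period to recurrence only, not to safety.
- **Event.** Write one criterion for seriousness so that heading and definition agree, and count serious adverse events in both arms, including those attributed to AAD.
- **Ascertainment.** Describe in sections 5.1 and 5.2 the same event collection for every patient in both arms. The 1-, 3-, 6- and 12-month points of section 5.2 and a common form would serve. The exact schedule matters less than its being identical.
- **Analysis.** Compare serious adverse events, death, HF hospitalization and the composite between arms over the common window. Report procedure-related complications descriptively for the ablation arm.
- **Limits.** State that allocation is non-randomized, so this makes counting symmetric without removing confounding. If follow-up has already finished, state how drug-arm events were or will be ascertained retrospectively, and that capture may be incomplete.

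The cost is wording in sections 5.1, 5.2 and 6. Where prospective contact is still possible, there would also be up to four contacts per drug-arm patient and per ablation patient outside the reconsented subset; the existing telephone interviews may cover part of the latter. Rewording without a drug-arm collection schedule would still under-count. Ablation may look safer or less safe than under the present text.
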